10.6 Appendix 4: Protocol Amendment history

The [PROTOCOL AMENDMENT SUMMARY OF CHANGES](#) for the current amendment is located directly before the [TABLE OF CONTENTS](#).

MedDRA	Medical Dictionary for Regulatory Activities
MRI	Magnetic Resonance Imaging
NC	Not Calculated
NCI-CTCAE	National Cancer Institute-Common Terminology Criteria for AEs
NE	Not Evaluable
N-RAS	Neuroblastoma Rat Sarcoma Viral Oncogene Homolog
ORR	Objective response rate (according to RECIST)
OS	Overall Survival
PD	Progressive Disease
PFS	Progression-free Survival (according to RECIST)
PFS2	PFS on Next-line Anti-cancer Treatment
PK	Pharmacokinetic
PP	Per Protocol
PR	Partial Response
PT	Preferred Term
QTcB	Bazett Corrected QT Interval
QTcF	Fridericia Corrected QT Interval
R _{C2h} , R _{Ctrough}	Accumulation Ratio of C _{2h} or C _{trough} on Cycle 3 Day 1/Cycle 1 Day 1
RECIST	Response Evaluation Criteria in Solid Tumors
RP2D	Recommended Phase 2 Dose
SAE	Serious AE
SAP	Statistical Analysis Plan
SBP	Systolic BP
SD	Standard Deviation
SD	Stable Disease
SI	International System of Units
SOC	System Organ Class
TFLs	Tables, Figures and Listings
T _{last}	Time of the Last Measurable Concentration
T _{max}	Time to Maximum Concentration
TEAE	Treatment Emergent Adverse Event
TESAE	Treatment Emergent SAE
TtP	Time to Progression (according to RECIST)
TtR	Time to Response (according to RECIST)
ULN	Upper Limit of Normal Reference Range

1. Source Documents

The Statistical Analysis Plan (SAP) was written based on the following documentation:

Document	Date	Version
Protocol	09Mar2023	Protocol Amendment 1
eCRF	03May2023	3.0

2. Protocol Details

2.1. Overall Study Design

Study SC105 (AURELIO-05) is a phase 2, open-label, single-arm, multicenter study with an initial safety run-in with 3+3 safety cohorts.

First, 3 patients will be recruited sequentially so that the first administrations of nanrilefusp alfa to the first and second patients will be 7 days apart and the second and third patients will not be dosed on the same day. These patients will be treated with cetuximab in combination with 9 µg/kg nanrilefusp alfa, a dose one dose level below the Recommended Phase 2 Dose (RP2D) as determined in study SC103 (AURELIO-03) which evaluated nanrilefusp alfa at doses up to 12 µg/kg in combination with pembrolizumab.

After the last patient in the 9 µg/kg safety cohort completes the first treatment cycle of 21 days, i.e., the Dose-Limiting Toxicity (DLT) assessment period, an Internal Safety Committee (ISC) will review the safety data. If at least one patient in the initial 9 µg/kg safety cohort experiences a DLT, an additional 3 patients will be recruited into the 9 µg/kg safety cohort. The ISC will review the safety data of these 3 additional patients and decide whether it is safe to increase the dose to 12 µg/kg nanrilefusp alfa in combination with cetuximab in the second safety cohort or whether the study should proceed with 9 µg/kg nanrilefusp alfa or with 6 µg/kg nanrilefusp alfa.

If there are no safety concerns in the initial 9 µg/kg safety cohort, the study will proceed to the second safety cohort and sequentially recruit another 3 patients who will receive 12 µg/kg nanrilefusp alfa in combination with cetuximab. As in the 9 µg/kg cohort, the first administrations of nanrilefusp alfa to the first and second patients will be 7 days apart and the second and third patients will not be dosed on the same day. Safety in the 12 µg/kg cohort will be evaluated by the ISC after the last patient completes the DLT assessment period (first treatment cycle of 21 days).

If at least one patient in the 12 µg/kg safety cohort experiences a DLT, an additional 3 patients will be recruited into the 12 µg/kg safety cohort. The ISC will review the safety data of these 3 additional patients and decide whether it is safe to proceed to the main cohort with patients receiving 12 µg/kg nanrilefusp alfa in combination with cetuximab or whether the study should continue at a lower nanrilefusp alfa dose.

If there are no safety concerns in the 12 µg/kg safety cohort, the study will proceed to the main cohort and recruit patients who will receive 12 µg/kg nanrilefusp alfa in combination with cetuximab.

Patients in the initial 9 µg/kg safety cohort may also have a dose increase to 12 µg/kg nanrilefusp alfa in the next treatment cycle at the discretion of the investigator if there are no safety concerns in the 12 µg/kg safety cohort.

Patients in the safety cohorts who do not fulfill the DLT evaluability criteria for any reason other than DLT during the DLT assessment period will be replaced until at least 3 patients per cohort have completed their DLT assessment period.

In the main cohort of the study patients will be treated with nanrilkefusp alfa in combination with cetuximab in 21-day cycles as described in the study protocol. An Independent Data Monitoring Committee (IDMC) will be established to review safety and efficacy data at certain time intervals, or when the interim analysis for futility is triggered, once the main cohort of the study starts.

Study periods

Participation of each patient will consist of the below study periods.

2.1.1. Study Intervention during Treatment Period

During the treatment period, study interventions will be administered as described in

[Table 1](#) and protocol section 6 until any of the criteria for discontinuation of study interventions is met.

Table 1 Study interventions

Intervention name and type	Dosage formulation	Unit dose strength(s)	Dosage level(s)	Route of administration	Regimen/treatment period	Sourcing
nanrilkefusp alfa Investigational intervention	Solution for injection	1.3 mg/vial	See section 4.1.1 of the protocol	Subcutaneous	Administration on day 1 (from cycle 2 onwards, ± 1 day), day 2 (± 1 day), day 8 (± 1 day), and day 9 (± 1 day) of each 21-day cycle	Provided centrally

Intervention name and type	Dosage formulation	Unit dose strength(s)	Dosage level(s)	Route of administration	Regimen/treatment period	Sourcing
Cetuximab Investigational intervention	Solution for infusion	5 mg/mL	Initial dose: 400 mg/m ² body surface area (BSA) as intravenous infusion over 120 minutes Subsequent doses: 250 mg/m ² as intravenous infusion over 60 minutes	Intravenous infusion via peripheral or central venous line	Administration on day 1 (from cycle 2 onwards, ± 1 day), day 8 (± 1 day), and day 15 (± 1 day) of each 21-day cycle; on day 1 and day 8, cetuximab infusion will start within 30 minutes after nanrilkefusp alfa administration	Provided centrally

After discontinuation of study interventions, patients will be evaluated at an end of treatment visit. This visit will be scheduled within 7 days (+7 days) after the patients' last dose of nanrilkefusp alfa and/or cetuximab (whichever occurs later).

2.1.2. Follow-up

All patients will come to the clinic 30 (± 2) days after their last dose of nanrilkefusp alfa and/or cetuximab (whichever occurs later).

Patients will be contacted 90 (+2) days after their last dose of nanrilkefusp alfa and/or cetuximab (whichever occurs later) and then followed up for survival at 3-month (± 2 weeks) intervals until the end of the study.

2.2. Study Objectives

2.2.1. Primary Objective

The primary objective of the study is to estimate the antitumor efficacy of nanrilkefusp alfa in combination with cetuximab.

2.2.2. Secondary Objectives

The secondary objectives of the study are:

- To further evaluate the antitumor efficacy of nanrilkefusp alfa in combination with cetuximab
- To assess the safety and tolerability of nanrilkefusp alfa in combination with cetuximab
- To determine the RP2D of nanrilkefusp alfa in combination with cetuximab
- To characterize the Pharmacokinetics (PK) of nanrilkefusp alfa in a subset of patients
- To determine the immunogenicity of nanrilkefusp alfa in combination with cetuximab

2.2.3. Exploratory Objectives

The exploratory objectives of the study are:

- To further evaluate the antitumor efficacy of nanrilkefusp alfa in combination with cetuximab
- To determine the status of immune-, molecular-, and disease-related biomarkers of potential importance
- To determine the impact of the Epidermal Growth Factor Receptor (EGFR) mutational status on efficacy
- To characterize the PK of cetuximab in a subset of patients
- To determine the immunogenicity of cetuximab in combination with nanrilkefusp alfa

2.3. Sample Size and Power

In the safety cohorts the traditional 3+3 design dose escalation will be applied. Therefore, 3 to 6 DLT-evaluable patients per dose level will be included in a cohort. The estimated number of patients is 6-12. The overall sample determined in this trial is 52 patients in efficacy population which includes patients from the safety cohorts and the main cohort.

The total sample size is based on a Bayesian calculation: Markov chain Monte Carlo has been used for the sample size determination. Assuming a desired Objective Response Rate (ORR) for the number of responses, and a uniform prior distribution between 0 and 1, the sample size of 52 patients will ensure at least 80% posterior probability to achieve an effect above the minimal ORR:

- Benchmark ORR: 20%¹
- Minimal ORR (relative increase, absolute increase): 28.8% (1.44, 8.8%)
- Desired ORR (relative increase, absolute increase): 36.8% (1.84, 16.8%)

2.4. Primary Efficacy Variable

The primary efficacy variable will be the ORR according to Response Evaluation Criteria in Solid Tumors version 1.1 (RECIST 1.1).²

2.5. Secondary Efficacy Variables

The secondary efficacy variables will be:

1. ORR according to immune-based Therapeutics RECIST (iRECIST)³ (iORR)
2. Best Overall Response according to RECIST 1.1 (BOR) and iRECIST (iBOR)
3. Duration of Response according to RECIST 1.1 (DoR) and iRECIST (iDoR)
4. Clinical Benefit Rate according to RECIST 1.1 (CBR) and iRECIST (iCBR)
5. Progression-Free Survival (PFS) according to RECIST 1.1 and iRECIST (iPFS)
6. Time to Response according to RECIST 1.1 (TtR) and iRECIST (iTtR)
7. Time to Progression according to RECIST 1.1 (TtP) and iRECIST (iTtP)

2.6. Exploratory Efficacy Variables

The exploratory efficacy variables will be:

8. PFS on Next-line Anti-cancer Treatment (PFS2)
9. Overall Survival (OS)
10. Assessment of Fragment crystallizable (Fc) gamma receptor polymorphism or presence and changes in T-cell clonality, levels of inflammatory/regulatory cytokines or circulating tumor markers such as circulating tumor Deoxyribonucleic Acid (DNA) at screening and following nanrilkefusp alfa and cetuximab treatment
11. Assessment of the EGFR mutational status at baseline and at disease progression

2.7. Safety Variables

The safety variables will be:

- Treatment-Emergent Adverse Events (TEAEs) according to the National Cancer Institute-Common Terminology Criteria for AEs (NCI-CTCAE⁴), version 5.0
- Safety laboratory findings
- Vital signs
- Electrocardiography findings
- DLTs

2.8. PK and Immunogenicity Variables

- Serum concentrations and calculated PK parameters of nanrilkefusp alfa and cetuximab (serum PK samples will be collected from all patients in the initial safety cohorts and from the first 12 patients in the main cohort)
- Incidence, titer, and time course of Anti-drug Antibodies (ADAs) against nanrilkefusp alfa, including neutralizing ADAs
- Incidence, titer, and time course of ADAs against cetuximab, including neutralizing ADAs

3. Analysis Populations

In accordance with ICH E3⁵ and ICH E9⁶, the following analysis sets will be used for the analyses.

3.1. Screened Population

The Screened Population will consist of all participants who signed the ICF.

The Screened Population will be used for the listing of screen failures and summaries of patient disposition and reasons for screening failures.

3.2. Enrolled Population

The enrolled population is defined as all patients who sign the main study informed consent form and all eligibility criteria are met as confirmed by approver during screening assessments.

This population may include patients who do not receive study treatment.

3.3. All-Subjects-as-Treated Population

The All-Subjects-as-Treated (ASaT) population will consist of all patients exposed to nanrilkefusp alfa or cetuximab.

All safety analyses will be performed on the ASaT population. The ASaT population will also be used for selected efficacy analyses.

3.4. Efficacy Population

The Efficacy population will consist of all patients exposed to the combination therapy for at least one treatment cycle. This is defined as patients with 4 doses of nanrilkefusp alfa and 3 doses of cetuximab in Cycle 1, or patients exposed to both nanrilkefusp alfa and cetuximab in Cycle 1 who started Cycle 2.

This will be the main population for the analyses of the primary endpoint and secondary efficacy endpoints.

3.5. Per Protocol Population

The Per Protocol (PP) population will consist of all patients who had at least one full treatment cycle of nanrilkefusp alfa and cetuximab (with 4 doses of nanrilkefusp alfa and 3 dose of cetuximab in Cycle 1), did not violate any eligibility criteria, and did not have any relevant major protocol deviations.

Protocol deviations are defined as any change, divergence, or departure from the study design or procedures defined in the study protocol. Important protocol deviations are a subset of

protocol deviations which may significantly impact the correctness, accuracy, and/ or reliability of the study data or that may significantly affect a patient's rights, safety, or well-being. [Section 3.5.1](#) details the deviations.

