6.5 Dose modification and toxicity management

6.5.1 Dose modification and toxicity management for nanrilefusp alfa

Dose modification and toxicity management for nanrilefusp alfa for safety reasons, will be discussed on a case-by-case basis between the site and the sponsor's medical monitor. Recommendations for clinical management of cytokine release syndrome are provided in [Table 6.4](#).

To minimize the risk for injection site reaction, subcutaneous injection sites should be rotated to different areas of the body (upper and lower extremities, each of the 4 quadrants of the abdomen) to minimize the summated local effects of nanrilefusp alfa administration.

To minimize the risks associated with shortening of the QT interval, vital signs and electrocardiography (ECG) must be closely monitored as per Protocol and institutional guidelines.

Liver function tests for nanrilefusp alfa toxicity evaluation in this study will include AST, ALT, total bilirubin, and alkaline phosphatase.

Nanrilefusp alfa-related hepatic toxicities should be managed as shown in [Table 6.2](#).

Table 6.2: Management of nanrilkefusp alfa-related hepatic toxicities

Nanrilkefusp alfa-related hepatic toxicity	Severity	Nanrilkefusp alfa dose modification
AST increased or ALT increased, or blood bilirubin increased	Grade 2 with AST or ALT >3 to $\leq 5 \times \text{ULN}$ or total bilirubin >1.5 to $\leq 3 \times \text{ULN}$	Withhold nanrilkefusp alfa Resume nanrilkefusp alfa if increased values return to grade ≤ 1
	Grade ≥ 3 with AST or ALT $>5 \times \text{ULN}$ or total bilirubin $>3 \times \text{ULN}$	Withhold nanrilkefusp alfa Resume nanrilkefusp alfa at one dose level below or reduce by 3 $\mu\text{g}/\text{kg}$ if increased values return to grade ≤ 1 Permanently discontinue nanrilkefusp alfa on second occurrence of grade ≥ 3 hepatic event

Please also refer to the IB, section 6.6 (Management guidelines for identified and potential risks).

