6.5.2 Dose modification and toxicity management for cetuximab

Cetuximab should be reduced, delayed, or discontinued to manage adverse reactions as described in [Table 6.3](#).

Table 6.3: Recommended dose modifications of cetuximab for adverse reactions

Adverse reaction	Severity (CTCAE, version 5.0)	Dose modification
Infusion reactions	Grade 1	Reduce the infusion rate by 50%. Infuse under close supervision.
	Grade 2	Reduce the infusion rate by 50%. Immediately administer treatment for symptoms.
	Grade 3 or 4	Immediately stop infusion and permanently discontinue cetuximab.
Dermatologic toxicities and infectious sequelae (e.g., acneiform rash,	First occurrence; grade 3 or 4	Delay infusion 1 to 2 weeks; if condition improves to grade ≤ 2 , continue at 250 mg/m^2 . If no improvement, discontinue cetuximab permanently.

Adverse reaction	Severity (CTCAE, version 5.0)	Dose modification
mucocutaneous disease)	Second occurrence; grade 3 or 4	Delay infusion 1 to 2 weeks; if condition improves to grade ≤ 2 , continue at 200 mg/m^2 . If no improvement, discontinue cetuximab permanently.
	Third occurrence; grade 3 or 4	Delay infusion 1 to 2 weeks; if condition improves to grade ≤ 2 , continue at 150 mg/m^2 . If no improvement, discontinue cetuximab permanently.
	Fourth occurrence; grade 3 or 4	Discontinue cetuximab permanently.
Pulmonary toxicity	Acute onset or worsening pulmonary symptoms	Delay infusion 1 to 2 weeks; if condition improves, continue at the dose that was being administered at the time of occurrence. If no improvement in 2 weeks or interstitial lung disease is confirmed, discontinue cetuximab permanently.
Ulcerative keratitis	Confirmed diagnosis	Interrupt or discontinue cetuximab permanently.

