9.2.4 Per Protocol population

The per Protocol (PP) population is defined as all patients who had at least one full treatment cycle of nanrilkefusp alfa and cetuximab, did not violate any eligibility criteria, and did not have any relevant major Protocol deviations.

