3.5.1. Important Protocol Deviations Leading to Exclusion from the PP Population

Deviations from the protocol, as defined in the protocol and/or protocol deviation plan, will be documented by the study monitors and project management throughout the study period.

Only those important protocol deviations considered to have a major effect on efficacy will lead to complete exclusion of the patient from the PP population. For the purposes of this study important protocol deviations leading to exclusion from the PP population will be defined. Criteria which require clinical or medical monitoring interpretation will be reviewed prior to database lock during data review meetings. All important protocol deviations leading to exclusion from the PP population occurring during the study will be reviewed and approved by sponsor prior to database lock in a separate document.

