5.5.2. Sensitivity for the Primary Analyses

Primary efficacy analysis will be repeated for ASaT and PP populations.

Primary efficacy analysis will be repeated where patients with missing data will be excluded from the analysis.

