5.9. Biomarkers

Biomarker collection data from eCRF will be listed for screened population. Biomarkers results will be reported separately for the CSR.

6. Changes in the Conduct of the Study or Planned Analysis

The following changes or precisions from protocol specified statistical analyses are made in this SAP.

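### SAP 3.5 ties the per-protocol set to full dosing in Cycle 1, where Protocol 9.2.4 accepts a full cycle at any time, and SAP section 6 does not list the change

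*SAP*

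**What the plan says.** Protocol 9.2.4 defines the PP set by three conditions: an exposure condition, no eligibility violation, and no relevant major deviation. The exposure condition covers "all patients who had at least one full treatment cycle of nanrilkefusp alfa and cetuximab". It names no cycle and gives no dose count.

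SAP 3.5 keeps the three conditions but qualifies the first in parentheses: "with 4 doses of nanrilkefusp alfa and 3 dose of cetuximab in Cycle 1".

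The neighbouring SAP definitions are wider. For the efficacy population, SAP 3.4 uses the same dose count but adds a second route: "or patients exposed to both nanrilkefusp alfa and cetuximab in Cycle 1 who started Cycle 2". The completed-cycle definition in SAP 5.6.1 likewise accepts a patient who has gone on to the next cycle. SAP 3.5 has no second route.

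The protocol foresees missed doses. For hepatic toxicity of grade 2 or higher, Table 6.2 says "Withhold nanrilkefusp alfa" until recovery. For grade 3 or 4 skin toxicity, among other reactions, Table 6.3 says "Delay infusion 1 to 2 weeks".

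The PP set is used in SAP 5.5.2: "Primary efficacy analysis will be repeated for ASaT and PP populations". It is used again for BOR/iBOR (5.5.3.1), iORR (5.5.3.2) and CBR/iCBR (5.5.3.4).

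SAP section 6 opens with "The following changes or precisions from protocol specified statistical analyses are made in this SAP" and then gives three items: the stable-disease derivation, duration of follow-up, and PK parameters.

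**The concern.** The SAP turns a requirement for one full cycle at any time into a requirement about the first cycle. A patient whose early dose was held for toxicity, and who was later treated in full and without deviation, belongs to the protocol's PP set but not to the SAP's.

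A PP repeat of the ORR is normally read as showing whether deviations or inadequate treatment moved the result. With the Cycle 1 condition, part of any difference from the main analysis would come from setting aside patients who had early toxicity but were treated in full afterwards. Because section 6 is silent, a reader of the protocol would not expect this.

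**Working it through.** **1. The SAP's dose count.** In each 21-day cycle the protocol schedules nanrilkefusp alfa on days 1, 2, 8 and 9 (4 doses) and cetuximab on days 1, 8 and 15 (3 doses). The 4 + 3 in the SAP is therefore one full scheduled cycle, 7 administrations. The count agrees with the protocol; the restriction to Cycle 1 does not.

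**2. Direction of the difference.** Anyone with 4 + 3 doses in Cycle 1 has had one full cycle. On the exposure condition the SAP set is therefore contained in the protocol set: the SAP can only remove patients, never add them.

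**3. A worked patient.** Day 8 and day 9 nanrilkefusp alfa are withheld for grade 2 hepatic toxicity under Table 6.2. Cycle 1 then has 2 of 4 nanrilkefusp alfa doses and 3 of 3 cetuximab doses. The patient recovers, receives all 7 doses in Cycle 2 and has no deviation.

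| Definition | Met? | Reason |
|---|---|---|
| SAP 3.4 efficacy population | Yes | both drugs in Cycle 1, Cycle 2 started |
| SAP 5.6.1 completed Cycle 1 | Yes | next cycle started |
| Protocol 9.2.4 PP | Yes | Cycle 2 is full |
| SAP 3.5 PP | No | 2 + 3 doses in Cycle 1 |

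**4. Who is lost through the SAP wording alone.** The protocol does not define a full cycle.
- If it means 4 + 3 doses, the natural reading, the loss is patients with an omitted Cycle 1 dose who later receive a full cycle. A patient who never has a full cycle fails both definitions.
- If it means a cycle completed in the SAP 5.6.1 sense, the loss is every patient with an omitted Cycle 1 dose who went on to Cycle 2.

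The worked patient is lost on either reading.

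**5. Size, by assumption only.** The documents give no rate of omitted Cycle 1 doses and no response rate in such patients. Take N = 52 in the efficacy population and R = 19 responders (0.368 × 52 = 19.1), with no other PP exclusions. The observed ORR is 19/52 = 36.5% (exact 95% CI 23.6 to 51.0). If k patients are dropped by the Cycle 1 condition and x of them responded, PP ORR = (19 − x)/(52 − k). Shifts are from unrounded values.

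| k (assumed share) | x = 0 | about 60% of the k responded |
|---|---|---|
| 3 (5%) | 19/49 = 38.8% (+2.2 points) | x = 2: 17/49 = 34.7% (−1.8) |
| 5 (10%) | 19/47 = 40.4% (+3.9) | x = 3: 16/47 = 34.0% (−2.5) |
| 10 (20%) | 19/42 = 45.2% (+8.7) | x = 6: 13/42 = 31.0% (−5.6) |
| 16 (30%) | 19/36 = 52.8% (+16.2) | x = 10: 9/36 = 25.0% (−11.5) |

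If the dropped patients respond much like the rest, little moves: k = 5, x = 2 gives 17/47 = 36.2% (−0.4), and k = 10, x = 4 gives 15/42 = 35.7% (−0.8). The table shows how the shift depends on k and x; it predicts neither.

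**The case against.** The case for leaving the text alone is that the affected group may be small and that nothing hangs on it. Much of this stands.

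- **The guidance is not absolute.** Table 6.2 says toxicities should be managed as shown, and Table 6.3 is headed as recommendations. A reader might say that the SAP drops patients for doing what the protocol requires; the wording is softer than that.
- **Only omitted doses matter.** A reduced dose is still a dose. A delayed dose may still count: SAP 4.1.1 takes the cycle from the CRF, and SAP 5.6.1 ends a cycle the day before the next begins, so a cycle can run past 21 days. The documents do not settle this.
- **Selection on tolerance is not wholly the SAP's doing.** Any full-cycle condition selects partly on tolerance, and the protocol has one. The SAP adds the tie to Cycle 1.
- **The exclusions will be visible.** SAP 5.2 reports the number excluded from PP with reasons, and lists the patients. This makes a difference traceable but does not restore the set that the protocol defined.

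Three stronger readings are tempting and are not supported. A reader might infer that doses withheld under section 6.5 should count as given; Protocol 9.2.4 credits no omitted dose, so that would be a new definition. A reader might set the shifts above against the distance between the minimal and desired ORR; no decision uses the PP set, so that comparison has no consequence in this plan. A reader might also see a conflict over eligibility violations between SAP 3.5 and 3.5.1, where "Only those important protocol deviations considered to have a major effect on efficacy will lead to complete exclusion"; that sentence can be read as elaborating only the deviation condition, which leaves eligibility as a separate condition.

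None of this answers the worked patient. Nor can the restriction pass as mere clarification that needs no entry, because section 6 covers precisions as well as changes.

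**Conclusion.** The point holds as an unlisted mismatch between the two documents. SAP 3.5 is narrower than Protocol 9.2.4, and it removes patients with an omitted Cycle 1 dose and a later full cycle who meet the protocol's definition. The PP repeats of ORR, BOR/iBOR, iORR and CBR/iCBR then depend partly on Cycle 1 tolerance.

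The reach is limited. The primary ORR uses the efficacy population, which keeps these patients once they start Cycle 2. The repeat in the all-subjects-as-treated population keeps everyone treated. The futility rule uses the efficacy population, and no hypothesis is tested. A reader might infer that the primary result or the stopping rule is compromised; neither is.

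The size and direction of any shift are unknown. That the mismatch exists rests on the text alone; the figures rest on assumed counts of dropped patients and of responders among them.

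**What to change.** In SAP 3.5, replace the words that tie the 4 + 3 doses to Cycle 1 with *in at least one cycle*, so that the exposure condition matches Protocol 9.2.4. Derive the PP flag on that basis before database lock.

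The cost is one phrase and one flag derivation. The PP set can only stay the same or grow. No protocol amendment is needed, since the change brings the SAP back to the protocol's definition. If the Cycle 1 restriction was deliberate, the minimum is to list it in SAP section 6 with the reason.
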